A randomized, double-blind, placebo-controlled efficacy and safety trial of FLU-v administered as 2 vaccinations or 1 vaccination vs placebo prior to intranasal challenge with the Influenza A 2009 H1N1 human virus.

In this study, the main efficacy comparisons are for each of the FLU-v groups to placebo. The study will not compare the two FLU-v dosing arms as the study may not have enough power to detect a significant difference in the primary efficacy endpoint of mild to moderate influenza induced disease (MMID) rates between the FLU-v groups.

2 Current Approved Study Protocol

The current approved study protocol is version 3.0 dated 18APR2017.

3 Study Hypothesis

The hypothesis is that vaccination with one dose or two doses of FLU-v + adjuvant will significantly reduce MMID when compared to individuals vaccinated with placebo.

4 Sample Size Justification and Analysis Plan

Sample size was calculated for 3 groups, a placebo group and 2 Investigational Medicinal Product (IMP) (i.e. one dose and two doses of FLU-v) groups. Each FLU-v arm will be compared to the placebo arm. Groups are randomized 1:1:1. All comparisons are at the 0.05 one-sided alpha level, and any p-value less than 0.05 would be considered as significant. This may increase the type-I error rate of potentially moving forward with an inactive treatment, but is appropriate for an early phase II trial of this type. Sample sizes assuming two different placebo MMID rates and for 80% power are given in Table 1 below.

Table 1.

Probability (rate) of MMID		Sample size per arm	Total sample size	Power	One-sided alpha
Placebo	Vaccine				
0.7	0.4	40	120	80%	0.05
0.8	0.5	37	111	80%	0.05

Table 1 shows that a sample size of 120 (40 per group) provides good power (80%) for a placebo MMID rate of 0.7 and an absolute reduction of 30%. The difference is clinically meaningful and the assumptions of a placebo MMID rate of 0.70 is reasonable and based on past experience.¹

5 Analysis Plan and Reports

The primary analysis population will be the Intent to Treat (ITT) population and will be used for the analysis of all primary and secondary endpoints. The ITT will include those participants who received both vaccination and challenge with an influenza virus.

The Per Protocol (PP) analysis population is defined as a subset of the ITT population who have no major protocol deviations (complied with the protocol appropriately in order to ensure that these data would be likely to reveal the effect of treatment). At a Blinded Data Review Meeting (BDRM), which will take place prior to database lock, ITT analysis set subjects will be reviewed for their inclusion/exclusion to the PP population.

Any participant who received at least one immunization but did not receive the influenza challenge virus will not be part of the ITT or PP analysis populations, but will be part of the safety population (SAF).

Subject disposition will be presented as a flow chart and will include number of subjects randomised, number of subjects that received one or two doses of FLU-v or placebo, number of vaccinated subjects that received the challenge virus, the number of subjects that withdrew from the study and the number of subjects that completed the study in each arm. Primary, secondary and safety endpoints will be presented in the clinical study report. Analysis and reporting of exploratory endpoints may be separate to the clinical study report.

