2 PROTOCOL SYNOPSIS

SYNOPSIS	
TITLE	Phase IIb Study of the Efficacy of FLU-v, a Broad Spectrum Influenza Vaccine in an H1N1 Influenza Healthy Human Challenge Model
SPONSOR	PepTcell Limited (t/a SEEK)
SPONSOR PROTOCOL NO.	FLU-v-004
PHASE	Phase IIb
INDICATION	Prophylaxis of Influenza
EUDRACT NUMBER	2016-002134-74
STUDY DESIGN	
A randomized, double-blind, placebo-controlled efficacy and safety trial of FLU-v administered as 2 vaccinations or 1 vaccination vs placebo prior to intranasal challenge with the Influenza A 2009 H1N1 human virus.
 
In this study, the main efficacy comparisons are for each of the FLU-v groups to placebo. The study will also compare the two FLU-v dosing arms but will only have power to detect a significant difference in Mild to Moderate Influenza Disease (MMID) rates between the FLU-v groups and placebo and not against each other.
 
Assuming significant efficacy of at least one dose of FLU-v against placebo is demonstrated in the current protocol (Part A), when the primary efficacy endpoint and key safety results are available, the protocol may be amended to include a second part (Part B) which will test the optimal FLU-v dose from Part A (in terms of efficacy and safety) versus current standard of care seasonal influenza vaccine. Details of Part B will be determined and documented in a future protocol amendment following the availability of the unblinded key efficacy and safety results from Part A. Approval will be sought via a substantial amendment from the competent authority before part B can commence.

SAMPLE SIZE	Up to 123 participants inoculated with the challenge virus
RANDOMISATION AND BLINDING	
Randomisation will occur on day -43.
 
Part A
 
FLU-v 1 or 2 doses and placebo treatment arms will be double-blinded and randomised 1:1:1.

SYNOPSIS	

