Assuming significant efficacy of at least one dose of FLU-v against placebo is demonstrated in the current protocol (Part A), when all the primary efficacy endpoint and key safety results are available, the protocol may be amended to include a second part (Part B) which will test the optimal FLU-v dose from Part A (in terms of efficacy and safety) versus current standard of care seasonal influenza vaccine. Details of Part B will be determined and documented in a future protocol amendment following the availability of the unblinded key efficacy and safety results from Part A. Approval will be sought via a substantial amendment from the competent authority before part B can commence

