9.3 Quarantine and Challenge

9.3.1 Visit 4 - Admission (Day -2 or Day -1 up to 40 days post second vaccination)

Subjects will be admitted to the Quarantine unit on day -2 or day -1 (minimum 20 days post second vaccination). If subject is not available to attend admission on the Day -2/Day -1 due date, the visit can be scheduled up to 40 days post second vaccination.

The admission procedures/assessments and testing will be performed after admission and before challenge virus administration. Study procedures will be conducted as detailed on the Time and Events schedule

As determined by the PI, results of standard procedures performed in the process of admission to the Quarantine unit may be used to determine suitability, including but not limited to vital signs, height, weight, etc. They can also be used to extend eligibility beyond 90 days from

screening if the participant has been vaccinated but his admission has fallen out of the 90 days window. A Viral Challenge serology test can be repeated if required before Quarantine if the participant has been vaccinated but the admission date has fallen out of the 90 days window. However, the serology test and result must be dated within 90 days of Day 0.

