5.2 Primary Endpoint: Incidence of MMID

MMID is defined as positive if a participant has both detectable shedding, as evaluated by RT-qPCR (reverse transcriptase quantitative polymerase chain reaction), and at least one symptom,

as observed on the Physician Assessment of Influenza Symptoms (PAI), at any time during subject quarantine, starting from the evening of Day 1 post-inoculation through the expected end of the quarantine period, Day 7, Discharge. The analysis of this endpoint will be performed by comparing the MMID rates in each of the FLU-v groups to the placebo group. Comparisons will be performed using one-sided Fisher's exact test, and the proportion of subjects with MMID and corresponding p-value will be presented. If a subject has no nasal swab data on two consecutive days, and the available recorded data shows no shedding, the MMID for that subject will be considered as missing. Similarly, if symptom data is not recorded on two consecutive days, and the available recorded data shows no symptoms, the MMID will be considered as missing for that subject. However, if a subject is positive for viral shedding and experiences at least one symptom with the available recorded data, that subject will be included in the MMID analysis. The primary analysis will incorporate missing data as described in section 5.7. The statistical summary data will be presented as tables and figures as described in sections 8-9 of this document.

5.3 Secondary Objectives:

To determine the overall effect of FLU-v on influenza disease based on disease severity measures (presence or absence of symptoms or shedding, symptom severity, symptom and shedding duration, total symptoms and shedding, and peak symptom and shedding). Viral shedding was evaluated by RT-qPCR and symptoms were evaluated by PAI, from the evening of Day 1 post-inoculation (more than 24 hours after inoculation) through the expected end of the quarantine period (Day 7, Discharge).

5.4 Secondary Endpoints:

- Overview of symptoms (PAI) and of viral shedding (RT-qPCR) from the evening of Day 1 post-inoculation (more than 24 hours after inoculation) through Day 7.

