5.8 Post-Hoc Analyses

Where possible all analyses will be prospectively planned and carried out according to this SAP. However, in the event of any significantly anomalous data or events which make any data or conclusions unreliable or scientifically questionable, then further relevant post-hoc analyses may be carried out. For example, but not limited to:

- Analysis of primary and secondary endpoints with removal of data from subjects where other respiratory infections have occurred concomitantly with the study challenge influenza virus (including 48 hours pre-inoculation and on day 2 or day 5 post-inoculation);
- Analysis of efficacy data including only subjects with an Haemagglutinin inhibition (HAI) titer for the challenge strain pre-inoculation lower than 40,
- Analysis of efficacy data comparing subjects whose HAI titer to the challenge strain rose from screening to pre-inoculation compared to those whose titer didn't change,

- Analysis with removal of data from subjects with any pre-existing heterotypic T-cell immunity to the study flu challenge virus,
- Due to the recall of atomisers in batch 160728, six subjects were inoculated with Challenge Virus with atomisers from the recalled batch, and 34 subjects were administered Challenge Virus using one atomiser per nostril rather than two atomisers per administration. Post-hoc analyses will be performed on the primary and secondary endpoints to assess whether there was any effect of the atomizer recall or/and from inoculating with one rather than two atomisers.
- Analysis of primary and secondary endpoint data (RT-qPCR and PAI) to include the data for subjects discharged from quarantine after Day 7.
- Analysis of the FLU-PRO secondary endpoint to include data for subjects discharged from quarantine after Day 7. This post-hoc analysis may also include reporting of proportion of symptomatic days and duration of symptoms for quarantine days.

6 Changes to the protocol-specified analyses

No changes to the protocol-specified analyses apart from the proposed and pre-defined post-hoc analyses.

There is a discrepancy between the sample size stated in the protocol and the sample size stated in Section 4 of this document. The protocol allowed for one additional subject per treatment group to account for unexpected subjects exclusion in the per protocol population due to a major protocol deviations.

7 References

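### The SAP drops the protocol's one-dose versus two-dose comparison and its 95% confidence interval, while SAP section 6 says the protocol-specified analyses are unchanged

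*SAP*

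**What the plan says.** **Protocol.** The synopsis states: "The study will also compare the two FLU-v dosing arms". Section 5.3 and section 16.2 repeat the commitment, and each time the text concedes that power for this contrast is inadequate. The statistics part of the synopsis and sections 16.4 and 16.5 promise 95% confidence intervals for the difference in MMID rates between the FLU-v groups. Section 16.2 sets all comparisons at a one-sided 0.05 level. Section 16.4 requires any departure from the protocol's analysis to be documented in a protocol or SAP amendment.

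The synopsis and sections 5.3 and 6.1 say that, if at least one FLU-v regimen is significantly better than placebo, the protocol may be amended to add a Part B, "which will test the optimal FLU-v dose from Part A (in terms of efficacy and safety"). Its details are left to that amendment.

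**SAP.** The opening design description reverses the first commitment: "The study will not compare the two FLU-v dosing arms". The reason given is that power may be insufficient. Section 4 says "All comparisons are at the 0.05 one-sided alpha level", and section 5.2 covers each FLU-v arm against placebo only: "Comparisons will be performed using one-sided Fisher's exact test, and the proportion of subjects with MMID and corresponding p-value will be presented". The SAP text contains no confidence interval for a difference between the FLU-v arms. Section 6 then states: "No changes to the protocol-specified analyses apart from the proposed and pre-defined post-hoc analyses". The same section does explain the difference of one subject per arm in sample size between the two documents.

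**The concern.** Two things are at issue.

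The first is documentary. A planned analysis and its interval have been removed, and the section meant to record such changes says there are none. A reader of the study report who relies on section 6 would not know that the comparison had been planned.

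The second is what Part A can say about the regimens. Which regimen is better is a question about the difference between the two FLU-v arms. Under the SAP the only inferential statements on MMID are two separate p-values against a shared placebo group. One can fall below 0.05 and the other above it when the regimens are equally effective, and without an interval for the direct difference the report gives no measure of how uncertain that contrast is. Low power is a good reason not to rely on a test of the contrast. It is not a reason to leave out the estimate, and the protocol had already accepted the low power when it planned the comparison.

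**Working it through.** **Inputs from the documents.** One-sided Fisher's exact test at 0.05 for each FLU-v arm against placebo, with no multiplicity adjustment (SAP sections 4 and 5.2; protocol section 16.2). Allocation 1:1:1 with one shared placebo arm. 40 per arm (SAP) or 41 per arm (protocol). Design MMID rates 0.70 on placebo and 0.40 on vaccine.

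**Assumption.** Both FLU-v arms have the same true rate. The documents do not state this scenario, so a range is shown.

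**Step 1: reproduce the plan's figures.** SAP section 4 says 40 per group "provides good power (80%) for a placebo MMID rate of 0.7 and an absolute reduction of 30" per cent. The normal-approximation sample size is

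n = [1.645·√(2·0.55·0.45) + 0.842·√(0.7·0.3 + 0.4·0.6)]² / 0.30² = (1.157 + 0.565)² / 0.09 ≈ 33.

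The continuity correction raises it to (32.95/4)·[1 + √(1 + 4/(32.95·0.30))]² ≈ 39.3, so 40, as the SAP states. The same formula gives the SAP's 37 for 0.80 v 0.50. Exact Fisher power by full enumeration is 0.798 with 40 per arm and 0.813 with 41, which agrees with the stated 80%.

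**Step 2: how often exactly one arm is significant.** Enumerate the three binomial counts, with the placebo count common to both tests:

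P(exactly one) = power(A) + power(B) − 2·P(both).

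At 0.70 / 0.40 / 0.40:
- 41 per arm: 2·0.8133 − 2·0.7036 = 0.219. Both are significant in 70.4% of trials and neither in 7.7%.
- 40 per arm: 2·0.7976 − 2·0.6820 = 0.231.

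| Placebo rate | Rate in both FLU-v arms | Exactly one significant, 40 per arm | Exactly one significant, 41 per arm |
|---|---|---|---|
| 0.70 | 0.30 | 5.6% | 4.9% |
| 0.70 | 0.40 | 23.1% | 21.9% |
| 0.70 | 0.44 | 30.1% | 29.4% |
| 0.70 | 0.47 | 33.0% | 32.9% |
| 0.70 | 0.50 | 33.0% | 33.5% |
| 0.70 | 0.70 (both inactive) | 4.7% | 4.8% |
| 0.80 | 0.50 | 19.2% | 18.5% |
| 0.60 | 0.30 | 22.3% | 21.0% |
| 0.50 | 0.21 | 22.4% | 21.4% |

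**Step 3: what the omitted interval would look like.** With both arms at 0.40, the 95% half-width is 1.96·√(2·0.4·0.6/41) = 0.212, or 0.215 with 40 per arm.

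**Step 4: would restoring the test help?** Little. With 41 per arm, a one-sided Fisher test of one FLU-v arm against the other has 17% power for 0.40 v 0.30 and 55% for 0.40 v 0.20.

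**Step 5: time from last FLU-v to challenge.** Protocol section 9.2.2 puts the second injection 21 to 28 days after the first. Section 9.3.1 puts admission at least 20 days after the second injection, and "the visit can be scheduled up to 40 days post second vaccination". Challenge follows admission by 1 or 2 days. Two-dose subjects are therefore challenged (20 to 40) + (1 to 2) = 21 to 42 days after their last FLU-v. One-dose subjects are challenged (21 to 28) + (21 to 42) = 42 to 70 days after theirs.

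**The case against.** The strongest reply is that this is a documentation gap with little practical effect. Several parts of it stand.

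- **A reader might infer that the SAP leaves the Part B choice to two p-values, so that an equally good regimen could be dropped for missing 0.05.** The documents do not say so. The protocol names efficacy and safety as the basis, gives no selection rule, and defers Part B to a later amendment. MMID proportions by arm, the secondary endpoints and the adverse events by group will all be reported.
- **The 22–23% is not a rate of wrong decisions.** It assumes equal regimens, so neither choice would be wrong on efficacy. With equal arm sizes and a shared placebo, the arm that is significant alone always has the lower observed MMID rate (enumerated for 40 and 41 per arm, no exceptions). Choosing on the point estimate would pick the same arm in those trials.
- **The interval would not always show compatibility with equality.** At 0.70 / 0.40 / 0.40 with 41 per arm, a Wald 95% interval for the direct difference excludes zero in 3.5 of the 21.9 percentage points, about one discordant trial in six.
- **A reader might also infer that the contrast is confounded by time to challenge.** The arms are randomised regimens and the timing is part of the regimen, so the comparison is valid for choosing between regimens. It cannot separate dose number from interval, which calls for a note at most.
- **The protocol's phrase about intervals between the FLU-v groups could have been meant as each group against placebo.** On that reading too, the SAP text contains no such interval. The shell tables are a separate document and were not available for this review.

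None of this removes the contradiction. The SAP cancels a comparison that the protocol promises, and section 6 says nothing changed.

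**Conclusion.** The point holds as an undeclared departure from the protocol with a modest inferential consequence. The SAP removes the planned comparison of the two FLU-v arms and its 95% interval, and section 6 is incorrect in reporting no change. What is lost is the only formal estimate of the difference between regimens, together with its uncertainty.

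The size of the interpretive risk depends on the true rates. Exactly one arm is significant in 22–23% of trials at the design rates with equal arms. The figure is about 5% when both arms are at 0.30 or both are inactive, and about 33% when both are near 0.50. These figures assume exact one-sided Fisher tests at 0.05, 40 or 41 per arm, a shared placebo arm and no missing outcomes. They show that a difference in significance is weak evidence of a difference between regimens. They do not show that the wrong regimen would be chosen, and the documents do not tie the choice to significance.

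**What to change.** 1. Restore in the SAP the two-dose minus one-dose difference in MMID rate with its 95% confidence interval, presented as an estimate and labelled low-power.
2. State beside it that a difference in significance against placebo is not evidence of a difference between regimens.
3. Correct SAP section 6. Record that the protocol's one-sided test of this contrast is replaced by estimation, and give the reason.
4. Optionally, note that the regimens differ both in dose number and in time from last FLU-v to challenge (21 to 42 v 42 to 70 days by the visit windows).

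The rule for choosing a regimen stays with the future Part B amendment, where the protocol places it.

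The cost is one table row and a few sentences in the SAP. No extra subjects are needed, and the primary tests and their alpha do not change. The small downside is that a wide interval, about ±0.21, will be on display.

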5.1 Primary Objective

To determine the effect of FLU-v in reducing the incidence of Mild to Moderate Influenza Induced Disease (MMID) defined as detectable viral shedding plus at least one symptom of influenza from Day 1 post-inoculation until Day 7. Day 1 post-inoculation evaluations were completed in the evening of Day 1, more than 24 hours post-inoculation.

5.2 Primary Endpoint: Incidence of MMID

MMID is defined as positive if a participant has both detectable shedding, as evaluated by RT-qPCR (reverse transcriptase quantitative polymerase chain reaction), and at least one symptom,

as observed on the Physician Assessment of Influenza Symptoms (PAI), at any time during subject quarantine, starting from the evening of Day 1 post-inoculation through the expected end of the quarantine period, Day 7, Discharge. The analysis of this endpoint will be performed by comparing the MMID rates in each of the FLU-v groups to the placebo group. Comparisons will be performed using one-sided Fisher's exact test, and the proportion of subjects with MMID and corresponding p-value will be presented. If a subject has no nasal swab data on two consecutive days, and the available recorded data shows no shedding, the MMID for that subject will be considered as missing. Similarly, if symptom data is not recorded on two consecutive days, and the available recorded data shows no symptoms, the MMID will be considered as missing for that subject. However, if a subject is positive for viral shedding and experiences at least one symptom with the available recorded data, that subject will be included in the MMID analysis. The primary analysis will incorporate missing data as described in section 5.7. The statistical summary data will be presented as tables and figures as described in sections 8-9 of this document.

5.3 Secondary Objectives:

To determine the overall effect of FLU-v on influenza disease based on disease severity measures (presence or absence of symptoms or shedding, symptom severity, symptom and shedding duration, total symptoms and shedding, and peak symptom and shedding). Viral shedding was evaluated by RT-qPCR and symptoms were evaluated by PAI, from the evening of Day 1 post-inoculation (more than 24 hours after inoculation) through the expected end of the quarantine period (Day 7, Discharge).

5.4 Secondary Endpoints:

- Overview of symptoms (PAI) and of viral shedding (RT-qPCR) from the evening of Day 1 post-inoculation (more than 24 hours after inoculation) through Day 7.
 - If a subject has no nasal swab data on two consecutive days, and the available recorded data shows no shedding, the endpoint will be considered as missing. Similarly, if symptom data is not recorded on two consecutive days, and the available recorded data shows no symptoms, the endpoint will be considered as missing for that subject. However, if a subject is positive for viral shedding with the available recorded data, that subject will be included in the analysis. Similarly, if the subject shows at least one symptom within the recorded data, that subject will be included in the analysis.

- Modified MMID
 - Incidence of at least two symptoms (on PAI) and viral shedding (RT-qPCR) at any time during the quarantine from evening of Day 1 post-inoculation through Day 7. If a subject has no nasal swab data on two consecutive days, and the available recorded data shows no shedding, the Modified MMID will be considered as missing. Similarly, if symptom data is not recorded on two consecutive days and the available recorded data shows no symptoms this endpoint will be considered as missing for that subject. However, if a subject is positive for viral shedding and experiences at least two symptoms with the available recorded data, that subject will be included in the modified MMID analysis.
- Viral shedding duration (days)
 - Measured from the first day with a positive test on RT-qPCR, starting from evening of Day 1 post-inoculation until the last day with a positive test during the expected quarantine period (up to Day 7). Intervening negative or missing test days will be included in the duration. If no positive test occurs, duration is counted as zero.
- Viral shedding quantitation (RT-qPCR)
 - Area under the curve (AUC) will be calculated based on each timepoint tested on RT-qPCR (log copy number/ml) record from evening of Day 1 post-inoculation to the morning of Day 7 (last timepoint before expected quarantine discharge) using Trapezoidal rule, and those samples below lower limit of quantification (LLOQ) will be replaced by half of LLOQ. Linear interpolation will be used for a single missing measurement. If more than one consecutive point is missing, the endpoint is considered as missing. RT-qPCR peak during entire quarantine period (i.e. the highest level of RT-qPCR recorded anytime during the quarantine period, starting from evening of Day 1 post-inoculation up to Day 7. A single maximum RT-qPCR (peak) will be identified for each subject during the quarantine on the assumption that a peak is recorded during the quarantine. Thus, there will not be imputation to predict the peak for subjects who have suspected missing peak data as it is implausible to predict the missing peak from the rest of the existing data.
- Symptom duration in days (PAI)
 - Number of days from first symptom noted, starting the evening of Day 1 post-inoculation until the day of last symptom noted up to Day 7. Intervening days with no symptoms or

missing symptom data will be included in the duration. If no symptoms occur during the entire period, number of days is zero.

- Total number of symptoms experienced (PAI)
 - Mean of total number of symptoms (upper and lower respiratory and systemic symptoms) experienced from the evening of Day 1 post-inoculation until the day of last symptom noted during the expected quarantine period (up to Day 7). Calculated as the total sum of symptoms experienced divided by the number of days in which symptoms were collected.
- Total symptoms score peak (PAI)
 - The highest level of the total sum of all upper and lower respiratory tract and systemic symptoms recorded on any day starting from the evening of Day 1 post-inoculation until the day of last symptom noted during the expected quarantine period (up to Day 7).
- Symptom severity score as measured by FLU-PRO Symptom Questionnaire
 - Mean of daily score over all study quarantine days from Day 1 post-inoculation to Day 7. If a day has missing data, this day will be excluded from the mean calculation (days with 0 as the symptom severity will be included in calculating the average).
- Comparison of each treatment group to placebo of the proportion of asymptomatic infected subjects defined as subjects with symptom score of zero (PAI) from Day 1 post-inoculation time-point through the expected end of quarantine (Day 7) with at least one positive result for viral shedding (RT-qPCR) in any of the quarantine days from the evening of Day 1 post-inoculation.
- Summary of Adverse Events from the Post-Vaccination Diary Card
 - The number of subjects who self-reported at least once any of the adverse events listed in the Post-Vaccination Diary Card during the 21 days following first vaccination and 21 days following second vaccination. Data will be presented for each treatment group by event and according to severity (mild, moderate, severe). The number of subjects in each treatment group with no self-reported events will also be presented.

The statistical software to be used for the analyses will be SAS (version 9.4) and R (version 3.43). The analyses of the secondary binary endpoints will be performed by comparing the rates in each of the FLU-v groups to the placebo group using one-sided Fisher's exact test. For all secondary endpoints, the primary analysis will assume missing data is missing at random so missing data will be ignored.

The analysis of all continuous secondary endpoints will be performed by calculating the median and interquartile range and then performing a one-sided Wilcoxon Rank Sum Test at 0.05 level of significance. These data will be reported as tables and figures as described in sections 8-9 of this document.

Statistical analysis will be performed by a junior statistician at NIAID-NIH and will be reviewed by the senior statistician. In addition, the Senior Clinical and Scientific Leader, will repeat the statistical analysis to validate the results.

